## **Objective**

To compare the impact of retropubic lidocaine versus normal saline on postoperative urinary retention in patients undergoing retropubic midurethral sling placement.

## **Background/Hypothesis**

Stress urinary incontinence (SUI) affects millions of women worldwide and has a profound impact on the quality of life of older individuals, their subjective health status, levels of depression and need for care. Midurethral sling placement was introduced in 1995 and remains the current gold standard for surgical management of SUI. Although the advantages of midurethral sling surgery include its high success rates and minimally invasive approach, approximately 10-50% of women experience acute postoperative urinary retention and are subsequently sent home with an indwelling foley catheter or clean intermittent self catheterization. Urinary retention is anxiety provoking for most patients and adds morbidity, cost, and increased utilization of healthcare resources. Additionally, catheterization of the urinary tract results in increased risk of urinary tract infection and potential need for antibiotics.

Several mechanisms could explain the inability to void postoperatively, including nerve conduction impairment from anesthesia. Multiple studies have investigated the use of various types of anesthesia and downstream effects on postoperative urinary retention. It is postulated that denervating the regional pelvic nerves for pain control may lead to denervation of the bladder for a transient period of time, blocking both the afferent and efferent pathways of the voiding mechanism, affecting the urethral retro-resistance pressure, and impacting urethral length thereby contributing to voiding dysfunction postoperatively.

Two of the most commonly used local anesthetic agents in surgical practice are lidocaine and bupivacaine. Lidocaine as a local anesthetic is characterized by a rapid onset of action, typically within 2-5 minutes of injection, and intermediate duration of efficacy. Therefore, it is often favored in the outpatient setting for pre-incisional injections. Of note, however, its effects generally only last up to 2 hours. Epinephrine (adrenaline) vasoconstricts arteries, delaying the resorption of lidocaine, and thus almost doubles the duration of anesthesia. Bupivacaine, on the other hand, has a slower onset of action, approximately 5-10 minutes after injection, but its effects last much longer, typically about 4-8 hours.

Our current practice of midurethral sling placement involves injection of lidocaine with epinephrine into the retropubic and suburethral space with the threefold purpose of hydrodissection, hemostasis, and pain reduction. Interestingly, several studies report varying rates of postoperative urinary retention and postoperative pain depending on the type of local anesthetic used (if any) for hydrodissection: however. the data is sparse and invites a more thorough investigation. For example, one study investigated the use of bupivacaine versus normal saline injected suburethrally on postoperative voiding function and pain in patients undergoing retropubic midurethral sling. These authors found no difference in voiding dysfunction between the study and placebo groups; however, the use of bupivacaine did lower pain scores at 6 hours postoperatively. A similar study compared urinary retention and pain control when bupivacaine versus saline for hydrodissection is used while placing tension-free vaginal tape midurethral slings. Hydrodissection fluid was placed subcutaneously, into the space of Retzius bilaterally, suburethrally, and periurethrally. These authors concluded that bupivacaine did not increase the risk of failing a postoperative voiding trial; however, there was a trend toward a difference with a 19% reduction in voiding trial success (47% pass rate in the bupivacaine group vs 66% in the saline only cohort, p = 0.14) and a statistically significant elevated PVR in the bupivacaine group compared with the control group. In addition, bupivacaine was not seen to improve immediate postoperative pain after placement of a tension-free vaginal tape. A third study reported that while bupivacaine did decrease postoperative pain scores following retropubic midurethral sling placement, reported pain was in fact low in both the intervention and placebo groups. Of note, there was also a trend toward increased voiding trial failure in the bupivacaine group (33% vs 18% in the controls (p = 0.082)). In this study, injections were performed into each of the two trocar paths "deep behind the pubic bone" and into the vaginal incision.

The aforementioned studies vary considerably in the quantity and composition of local anesthetic used intraoperatively, the location of injection, and in the administration of voiding trials postoperatively. Sample size of each study was also small and thus perhaps underpowered to detect statistically significant differences. Therefore, based on the limited existing data, we hypothesize that patients receiving retropubic normal saline compared to local anesthetic (e.g., lidocaine) will have a reduction in rates and duration of postoperative urinary retention following retropubic midurethral sling placement.

**Aim 1**: to compare the incidence of urinary retention following retropubic midurethral sling placement in those women receiving normal saline vs lidocaine for retropubic hydrodissection. We will compare rates of failed retrograde voiding trials between patients receiving normal saline and those receiving the same quantity of lidocaine. This will be completed using a standardized retrograde voiding trial 1-2 hours postoperatively (as outlined in "Data and Statistical Methods" below). We hypothesize that patients receiving normal saline will have a reduction in postoperative urinary retention following retropubic midurethral sling placement.

**Aim 2**: to assess postoperative pain in women receiving retropubic normal saline vs lidocaine during midurethral sling placement. Postoperatively, subjects will be asked to assess their pain using a VAS scale administered by nursing personnel at 2 hours (+/- 30 minutes) and again at 6 (+/- 30 minutes) hours following surgery, during the time of routine vital sign assessment. The subsequent pain assessments will be completed by the patient via an at-home form from discharge through postoperative day #7. Narcotic use will be queried through the electronic medical record as well as with a pain diary administered at time of discharge until postoperative day #7.

Aim 3: to examine differences in patient satisfaction and quality of life following retropubic midurethral sling placement between women receiving retropubic normal saline vs lidocaine at time of midurethral sling placement. Differences in patient satisfaction will be compared using multiple questionnaires at multiple time points. Patients will be asked to complete the American Pain Society Patient Outcome Questionnaire (APS-POQ-R) on POD #1. Patients will be asked to rate their satisfaction with surgery on a Likert scale (with 1 being the least satisfied and 5 being the most) at their 6-week postoperative follow up visit. We hypothesize that women receiving normal saline for hydrodissection will have improved patient satisfaction, mood, and quicker return to activities, as evidenced by lower APS- POQ-R scores and higher Likert scores compared to those receiving lidocaine.

## **Study Entry and Recruitment**

Subjects with stress incontinence or stress-predominant mixed urinary incontinence who are scheduled to undergo a retropubic midurethral sling with or without concomitant anterior repair at West Penn Hospital, Bethel Park Health and Wellness Pavilion, Wexford Health and Wellness Pavilion, and Jefferson Hospital of the Allegheny Health Network, will be offered participation in the study. Study subjects may also be recruited via the MyChart app. The MyChart app is a secure app accessible only by the patient. Only the patient can access their medical information through this app by setting up a secure account using their social security number, birthday, username, and password. The patient can log in securely by providing their username and password, or via biometrics (i.e., face recognition). If the research staff reaches out to the subject via telephone and the subject does not answer, a follow-up message will be sent to the subject via the MyChart app, with the statement that initial contact attempt was made by phone. The message will include the following:

A recent review of your records indicated that you may be eligible to participate in an ongoing research study. The Retropubic Lidocaine study is looking to determine if the numbing medicine we standardly use during surgery impacts your ability to empty your bladder postoperatively. If you are interested in participating, you would be randomly selected to get our standard numbering medicine (lidocaine and epinephrine) or placebo (saline and epinephrine) at the two sling exit sites in your pubic area while in the operating room. This study does not require any additional in-person visits. There will be a few questionnaires we would ask you to complete during your recovery. If you are interested in learning more about our study, please call [contact], or email [contact]. If you respond to this message indicating your interest, you are giving your permission for the study staff to receive your phone number and/or email address indicated in your medical records and reach out to you directly.

Inclusion criteria includes the following: age 18 years or older, English speaking, and competent to give consent. Exclusion criteria includes a known intolerance or allergic reaction to local anesthetics, planned spinal anesthesia for the procedure, planned concomitant prolapse repair other than anterior repair, or preoperative voiding dysfunction as evidenced by a post-void residual (PVR) of 150 mL or greater. On average, our institution treats 60-80 patients per year with midurethral slings.

Informed consent will be obtained at the preoperative appointment. Demographic information including age, weight, height, body mass index (BMI), allergies, obstetrical, gynecological, medical, and surgical history will be collected from those subjects who agree to participate. Preoperative bladder testing obtained as part of routine clinical care will also be recorded,

Patients will be randomized in the preoperative area on the day of surgery to prevent randomization of patients who may go on to cancel or postpone surgery. Randomization will be created using a random numbers table with blocking into groups of 4. On the day of surgery, the operating room pharmacist will prepare 20 cc of either study drug, 0.5% lidocaine with epinephrine 1:200,000, or normal saline with epinephrine 1:200,000 in identical appearing 20cc syringes to be injected retropubically. Our group's routine clinical practice will inject the randomly assigned 20cc syringe retropubically along the path of the midurethral sling trocars. Suburethral injection of local anesthetic will be performed at surgeon discretion. Surgical teams, anesthesia teams and patients will be blinded to allocation assignment. The investigational drug pharmacist will maintain the randomization sequence.

Standard postoperative care will then be followed. Before discharge, as part of routine clinical care, all subjects will undergo a postoperative voiding trial as outlined below. A routine postoperative evaluation will be performed by the primary surgeon at a 6-week interval following surgery.

Table 1. Timeline of data collection

	Time of Data Collection/Eval						itions	
Data	Baseline	Intervention	Surgery	Pos	stoperative as			
				2 h	6 h	24h	Week 1	Week 6
				(+-30	(+- 30			
				mins)	mins)			
Retrograde Voiding Trial				Х				
VAS pain score	Х			Х	Х			
Narcotic requirements	Х		Х	Х	Х	Х	х	
Pain Diary						Х	х	
Demographic factors	Х							
Intraoperative factors			Х					
Side effects (APS-POQ-R)						Х		
Satisfaction Likert Scale								Х
Patient satisfaction and						Х		
mood (APS-POQ-R)								

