#### Variables and measures

## Postoperative Urinary Retention

The primary outcome is postoperative voiding trial failure, defined as being discharged from the hospital with an indwelling catheter or instructions for clean intermittent self-catheterization (CISC). Duration of catheterization will also be measured and recorded on the postoperative diary. As part of routine clinical care, a retrograde voiding trial will be completed 1-2 hours postoperatively using the following protocol and parameters:

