## **Data and Statistical Methods**

**Aim 1**: to compare the incidence of urinary retention following retropubic midurethral sling placement in those women receiving normal saline vs lidocaine for retropubic hydrodissection. Rates of postoperative urinary retention will be compared between groups using chi squared testing. Duration of urinary retention measured in days will be compared using t-tests or nonparametric testing as appropriate. To adjust for other factors that may impact voiding trial results, logistic regression analysis will be performed and will include variables identified as significant (p>0.01) on univariable analysis as well as intraoperative narcotic use, age, and estimated blood loss. All analyses will be performed using intention to treat. Data analyses will be done using SPSS and Matlab.

**Aim 2**: to assess postoperative pain in women receiving retropubic normal saline vs lidocaine during midurethral sling placement. VAS scores will be measured on a scale of 0-100mm with higher scores indicating worse pain. Change from baseline in VAS pain scores will be compared at each time point with t-tests. Narcotic requirements measured in morphine equivalent grams will be compared by t-tests (and

Wilcoxon rank-sum tests if non-parametric). Both VAS pain scores and narcotic requirements will be compared in an intention to treat analysis. Multivariable logistic regression analyses will be used to identify independent risk factors that predict pain at 2, 6 and 24 hours postoperatively. We plan to adjust for operating time, estimated blood loss, urinary retention, and concomitant procedures, as all of these may predict worse postoperative pain. Anything found to be different at baseline will also be included as covariates.

**Aim 3**: to assess patient satisfaction in women receiving retropubic normal saline vs lidocaine during midurethral sling placement. Patient satisfaction Likert scale questionnaires will be compared using t-tests with lower scores indicating worse satisfaction. T-tests (and Wilcoxon rank-sum tests if non-parametric) will be used to analyze results of individual APS-POQ-R questions.

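### Planned anterior repair is neither a randomisation stratum nor a pre-specified Aim 1 covariate, although Aim 2 adjusts for concomitant procedures: a small, cheaply closed gap in precision

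*Combined protocol and SAP*

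**What the plan says.** Under Study Entry and Recruitment, the women offered participation are those "scheduled to undergo a retropubic midurethral sling with or without concomitant anterior repair". The exclusions in the same section remove women with "planned concomitant prolapse repair other than anterior repair". Randomisation takes place in the preoperative area on the day of surgery. On method the section says "Randomization will be created using a random numbers table with blocking into groups of 4" and names no stratification factor.

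Postoperative Urinary Retention defines the endpoint: "The primary outcome is postoperative voiding trial failure, defined as being discharged from the hospital with an indwelling catheter", or with instructions for self-catheterisation. For Aim 1, Data and Statistical Methods says "Rates of postoperative urinary retention will be compared between groups using chi squared testing". A logistic regression follows, containing "variables identified as significant (p>0.01) on univariable analysis as well as intraoperative narcotic use, age, and estimated blood loss". Concomitant procedure is not named there. For the Aim 2 pain models the same section says "We plan to adjust for operating time, estimated blood loss, urinary retention, and concomitant procedures". On the analysis set it says "All analyses will be performed using intention to treat".

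**The concern.** Planned anterior repair is fixed before allocation, and the eligibility text itself singles it out. The authors thought added procedures important enough to adjust for when modelling pain, but did not pre-specify them for the primary aim and give no reason. Two of the three covariates that the Aim 1 model does name, narcotic use during surgery and blood loss, are recorded only after randomisation.

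If anterior repair affects the voiding trial, an uneven split between arms would move the observed difference, and the plan has no agreed way to handle it. Whether the adjusted Aim 1 result accounts for it depends on a screen run on the outcome data. The printed criterion, p>0.01, read literally selects the variables that are not significant. At stake are a little precision and the clarity of the adjusted result, which matter most if the primary comparison is close.

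**Working it through.** **Inputs from the documents.** Retention 35%, reduction 20%, 80% power, two-sided alpha 0.05, 72 per arm, 75 after 5% loss (Sample Size Calculation).

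**Inputs assumed.** The share having anterior repair, q, is taken as 10-50%. The increase in voiding trial failure with anterior repair, D, is taken as 0-30 percentage points. The documents give neither.

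**Step 1: the plan's own figure.** Reading the 20% as percentage points (35% to 15%), with pooled variance and no continuity correction:

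n = [1.96·√(2·0.25·0.75) + 0.8416·√(0.35·0.65 + 0.15·0.85)]² / 0.20² = 72.4

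This rounds up to 73, against 72 stated. Then 72/0.95 = 75.8, or 76, against 75 stated. Both reproduce to within one. A relative reading (35% to 28%) would need 691 per arm, so the absolute reading is the one used. None of this depends on stratification.

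**Step 2: chance imbalance.** The difference between arms in the proportion having anterior repair has SD = √(2q(1−q)/72), and its 95% range is ±1.96·SD. For q = 0.3: √(0.42/72) = 0.076, and 1.96 × 0.076 = 0.150.

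**Step 3: shift in the observed difference.** Shift = imbalance × D. For q = 0.5 and D = 30 points: 0.163 × 30 = 4.9 points.

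**Step 4: error rate and power.** These come from 200,000 simulated trials per scenario, with 72 per arm and no stratification. The control rate is 35% overall, and a common odds ratio gives 15% in the other arm. The plain chi-squared test is compared with a Mantel-Haenszel test stratified by anterior repair, which stands in for adjustment.

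| q | 95% imbalance | Shift at that limit, D = 10 / 20 / 30 | Trials with imbalance ≥10 points | Power change from stratified test, D = 0 / 10 / 20 / 30 |
|---|---|---|---|---|
| 10% | ±9.8 | 1.0 / 2.0 / 2.9 | 4% | −0.8 / −0.7 / −0.3 / +0.4 |
| 20% | ±13.1 | 1.3 / 2.6 / 3.9 | 12% | −0.8 / −0.7 / 0.0 / +1.3 |
| 30% | ±15.0 | 1.5 / 3.0 / 4.5 | 17% | −0.8 / −0.6 / +0.3 / +1.9 |
| 50% | ±16.3 | 1.6 / 3.3 / 4.9 | 21% | −0.8 / −0.5 / +0.6 / +2.1 |

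Imbalance, shift and power change are in percentage points. With D = 0 the shift is zero. Type I error of the planned chi-squared test is 0.048-0.050 in every scenario and its power is about 81%. The stratified test has power of 80-83%.

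**Step 5: scale.** The standard error of the difference at 35% versus 15% is √((0.2275 + 0.1275)/72) = 0.070, or 7.0 points. The largest shift in the table, 4.9 points, is therefore below one standard error (4.9/7.0 = 0.7).

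**Step 6: can the screen be relied on?** Suppose p<0.01 was meant, which is an assumption. Take q = 30% and a 20-point effect in both arms, so 43.2 of 144 women have the repair and 25% fail overall. The univariable z is 0.20/√(0.25·0.75·(1/43.2 + 1/100.8)) = 0.20/0.0787 = 2.54, just short of the 2.58 required. A factor with an effect as large as the trial's target would be missed about half the time.

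**The case against.** The strongest reply is that nothing here is an error. Randomisation balances anterior repair on average, many two-arm trials of 150 do not stratify, and any chance imbalance is already part of the sampling error that the chi-squared test allows for. Enrolling both operations is a legitimate choice. All of this stands, and Step 4 supports it.

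A reader might go further than the documents allow in three ways.

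- **That the primary comparison is biased because different operations are mixed.** It is not. The shifts in Step 3 have mean zero, and the larger ones need both an extreme imbalance and an assumed effect as big as the trial's target or bigger.
- **That Aim 1 ignores anterior repair.** The logistic model admits variables that pass the univariable screen, so it could enter. What can be said is that its entry is not pre-specified and, with the criterion as printed, cannot be predicted.
- **That the exclusions let in women having other, non-prolapse surgery, so eligibility should be tightened.** The recruitment paragraph already limits the offer to a sling with or without anterior repair, and exclusions need not repeat that limit. Narrowing entry would also have a price: 60-80 sling patients a year over two years is 120-160 women, against 150 required.

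One part of the reply does not stand. The screen is no substitute for pre-specification, because it is data-driven, its printed criterion is unclear, and even a p<0.01 reading could miss a sizeable effect (Step 6).

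**Conclusion.** The point holds as a small matter of pre-specification and precision. A factor that is known before randomisation, and treated as relevant under Aim 2, is neither a stratum nor a fixed Aim 1 covariate. The primary test is valid and the sample size is unaffected.

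Under the assumed ranges in the working, the imbalance at its 95% limit is about ±10 to ±16 points, the resulting shift is 0 to about 5 points against a 20-point target, and the gain in power is at most about 2 points. If anterior repair has little or no effect on voiding, the stratified test gains nothing and gives up as much as 0.8 of a point. The case for changing the plan therefore rests mainly on fixing the adjusted analysis in advance at almost no cost, and only secondarily on power. All of these sizes depend on assumptions that the sponsor could replace with its own figures for the share having anterior repair and their retention rate.

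**What to change.** 1. In Data and Statistical Methods, Aim 1, name planned anterior repair (yes/no) as a fixed covariate in the logistic model, whatever the univariable screen shows. Use the operation planned at randomisation, so that the variable cannot be influenced by anything that happens afterwards.
2. If randomisation has not begun, also stratify the blocks of 4 by planned anterior repair and analyse Aim 1 by that stratum, for example with a Mantel-Haenszel test. If it has begun, item 1 alone is enough.

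No change to eligibility is needed.

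**Cost.** Item 1 adds one term to a model with about 36 expected failures (72 × 0.35 + 72 × 0.15 = 25.2 + 10.8). Item 2 needs a second pharmacy list. If few women have anterior repair, that stratum will be small (about 7 per arm at 10%, since 0.10 × 72 = 7.2) and its coefficient imprecise. If the repair has no effect on voiding, the loss is under 1 point of power.

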# Retrograde Voiding Trial:

- Confirm that all urine is drained from the bladder with the indwelling catheter in place
- Backfill 300 mL of sterile saline into the bladder through the indwelling catheter
- Clamp catheter, deflate the balloon, and remove the catheter
- The patient should be asked to void within 1 hour into a urine collection container in the toilet
- Record voided volume

Passed void trial: patient voids at least 200 mL Failed void trial: patient voids <200 mL or cannot void at all within 1 hour of test

In the event that all 300 mL of sterile saline are unable to be instilled into the bladder due to patient discomfort or bladder spasms, the test is still considered passed if >2/3 of instilled bladder volume is voided.

All patients who meet criteria for failure as described above are discharged from the hospital with either an indwelling catheter or CISC.

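### Preoperative PVR, admitted up to 149 mL and directly related to the voiding-trial endpoint, is not a prespecified covariate in the Aim 1 model

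*Combined protocol and SAP*

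**What the plan says.** **Entry.** Study Entry and Recruitment excludes "preoperative voiding dysfunction as evidenced by a post-void residual (PVR) of 150 mL or greater". It gives no bladder volume at which that residual is taken. The same section adds: "Preoperative bladder testing obtained as part of routine clinical care will also be recorded".

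**Endpoint.** Under Postoperative Urinary Retention: "The primary outcome is postoperative voiding trial failure, defined as being discharged from the hospital with an indwelling catheter" or with instructions for self-catheterisation. The Retrograde Voiding Trial section drains the bladder and then instructs staff to "Backfill 300 mL of sterile saline into the bladder through the indwelling catheter". The pass rule is "Passed void trial: patient voids at least 200 mL" and the failure rule is "patient voids <200 mL or cannot void at all within 1 hour of test". If the full volume cannot be instilled, "the test is still considered passed if >2/3 of instilled bladder volume is voided". Every woman who fails goes home with a catheter or self-catheterisation, so failing the trial is the primary event.

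**Analysis.** Data and Statistical Methods, Aim 1: "Rates of postoperative urinary retention will be compared between groups using chi squared testing". A logistic regression then adjusts for intraoperative narcotic use, age, estimated blood loss and whatever a univariable screen selects. The screen's criterion is printed as p>0.01. Preoperative PVR is not named. Table 1 schedules the retrograde voiding trial at 2 hours only, so there is no baseline result on the same test.

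**The concern.** The entry rule and the endpoint both concern incomplete emptying, but they draw the line in different places and in different units. A woman can count as free of voiding dysfunction at entry, empty her bladder no worse after surgery, and still be recorded as a case of postoperative retention. Such an event carries no information about lidocaine.

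The variable that identifies these women has to be known before the eligibility rule can be applied. It is fixed before randomisation and bears directly on the outcome. The plan nevertheless leaves its place in the adjusted analysis to a data-driven screen whose criterion is, as printed, the wrong way round. At stake are the precision of the adjusted comparison and how far the events can be attributed to the procedure or the anaesthetic.

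**Working it through.** **1. Residual implied by the failure rule.** The trial scores the volume voided, not the residual. Let R be the residual and u the urine made between filling and voiding, both in mL.

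- Void = 300 + u − R.
- Failure is a void below 200, that is R > 100 + u.

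New urine therefore makes passing easier. The documents give no urine output, so u is an assumption:

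| u (mL) | Residuals that fail but lie below 150 mL |
|---|---|
| 0 | 101–149 (void 151–199) |
| 25 | 126–149 |
| 49 or more | none |

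With an incomplete fill the limit falls. For a 240 mL fill, two thirds is 160 mL and a pass needs more than that, so a residual of 80 mL fails when u = 0.

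**2. Whether a preoperative PVR carries over to a 300 mL fill.** The plan gives no pre-void volume. Suppose, as an assumption, that a woman empties the same proportion each time and u = 0. She fails if PVR/(PVR + voided volume) exceeds 1/3, that is, if the volume she voided was less than twice her PVR.

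- PVR 120 after voiding 280: 280/400 = 70% emptied, so 210 of 300 mL voided. Pass.
- PVR 120 after voiding 150: 150/270 = 55.6% emptied, so about 167 of 300 mL voided. Fail.

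The same PVR can fall on either side. Overlap is possible for a given woman, but not certain.

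**3. The plan's sample size.** The plan states 72 per group for 80% power at two-sided 0.05, starting from 35% retention with a reduction of 20%. Read as 35% v 15%, with pooled rate 0.25:

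- n = [1.96·√(2·0.25·0.75) + 0.8416·√(0.35·0.65 + 0.15·0.85)]² / 0.20² = (1.2003 + 0.5014)² / 0.04 = 72.4.
- Rounded up this is 73. Power at 72 per group is 79.8%. The plan's figure reproduces.

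**4. What dilution would look like if it occurred.** Let f be the share of women who fail in both arms for this reason alone. The documents do not give f, so these rows are an illustration and not an estimate. In A the remaining women follow 35% v 15%: p1 = f + (1−f)·0.35 and p2 = f + (1−f)·0.15. In B the lidocaine rate stays at 35% including these women: p2 = f + (0.35−f)·15/35. Power is at 72 per group.

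| f | A: difference, power | B: difference, power |
|---|---|---|
| 0 | 20.0 points, 79.8% | 20.0 points, 79.8% |
| 2% | 19.6 points, 76.5% | 18.9 points, 74.2% |
| 5% | 19.0 points, 71.6% | 17.1 points, 64.8% |
| 10% | 18.0 points, 63.8% | 14.3 points, 48.1% |

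**5. The route by which PVR could enter the model.** Read literally, the screen admits variables with p above 0.01 and drops those below it, so a strongly predictive PVR would be left out. If the sign is a misprint for less-than, PVR enters only when the observed data reach p<0.01. Neither reading makes its inclusion prespecified.

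**The case against.** The case against is strong on several counts.

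- **Scale and scoring.** The endpoint counts voided volume, so new urine narrows the overlap and closes it near 49 mL for a full fill. The PVR has no pre-void volume. This stands. A reader might infer that every woman with a PVR of 101–149 mL fails whatever her treatment, or that the two limits contradict each other outright. The documents do not support that. One rule is an eligibility screen, the other a routine-care discharge test.
- **Size.** A reader might infer from step 4 that the trial is underpowered. That needs a value of f that appears nowhere, certain failure in both arms, and a planned reduction that makes no allowance for such women. The Sample Size Calculation does not show the last of these, since it uses the institution's overall rate. The low figures cannot be used as findings.
- **Bias.** Randomisation and blinding make such failures equally likely in the two arms. The comparison of discharge with a catheter remains valid whatever the baseline emptying.
- **Existing provision.** PVR can already enter through the univariable screen, and adding it to the logistic model leaves the chi-squared test unchanged. Both are true. But the screen is data-dependent and misprinted. The adjusted model is also the plan's own means of allowing for other influences on the voiding trial, and preoperative PVR is one of the more obvious of these.

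**Conclusion.** The point holds in a limited form. The thresholds allow some women with incomplete emptying at baseline to meet the primary endpoint with emptying unchanged by surgery or study drug. For a full fill the largest possible overlap is a residual of 101–149 mL, and it shrinks as urine is made. How many women this touches is unknown. The number could be negligible, and no loss of power should be quoted as fact. The effect, if present, is dilution of the difference and loss of precision, not bias toward saline or lidocaine.

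What the plan can be faulted for is narrower. A baseline variable directly related to the endpoint, and already obtained for eligibility, has no prespecified role in the analysis and depends on a screen that, as printed, would reject it if it mattered. This rests on the wording of Aim 1 alone and needs no assumption about f or u.

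**What to change.** In Data and Statistical Methods, Aim 1, name preoperative PVR as a continuous, prespecified covariate in the logistic model, included whatever its univariable result. This takes one sentence and no new data collection.

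The statistical cost is one degree of freedom. Under the plan's own rates, 72 per arm gives about 72·0.35 + 72·0.15 = 36 events. Treatment plus the three named covariates is four terms, or 9 events per term. Adding PVR makes five, or about 7.2. That is acceptable, but it is a reason to keep the screened additions few. The chi-squared test stays as the primary comparison.

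In Study Entry and Recruitment or Retrograde Voiding Trial, explain why the two limits differ or reconcile them, and say whether the preoperative PVR is taken at any standard bladder volume. This requires no change to eligibility or care, and no view is taken here on which limit is right.

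Optionally, add a supportive sensitivity analysis restricted to women with lower preoperative PVR. It reduces the sample, and any cut-off is only loosely tied to the 300 mL test, so it should not replace the continuous covariate.
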